Removed text describing sample size calculations as this study is not powered to detect differences between treatment groups.		Synopsis , Section 9.6
Added urine pregnancy tests for all site visits and an explanatory footnote indicating that serum pregnancy tests will be performed at the screening and withdrawal visits for the Double-blind Acute, Open-label Acute, and Double-blind Maintenance Study Phases; urine pregnancy tests will be conducted at all other site visits.		Schedule of Assessments (Table 1 , Table 2 , Table 3)
Clarified that all pregnancy tests will only be performed on females of childbearing potential.		Schedule of Assessments (Table 1 , Table 2 , Table 3), Section 4.4.1, Section 7.2.2.7
Added AE assessment during scheduled telephone calls and on Visit 5 (Table 3 only).		Schedule of Assessments (Table 1 , Table 2 , Table 3)

Protocol Amendments		
Summary of Change(s) Since Last Version of Approved Protocol		
Amendment Number	Amendment Date	Global/Country/Site Specific
5	10 Apr 2017	Global
Description of Change		Section(s) Affected by Change
Clarified footnote describing follow-up assessment to indicate that this will occur within 7 days of last dose of investigational product.		Schedule of Assessments (Table 1 , Table 2 , Table 3)
Expanded the window for acceptance of historical endoscopy results from 7 days to 21 days prior to the Screening Visit.		Schedule of Assessments (Table 1), Section 7.1.1.1 , Section 7.1.1.3 , Section 7.2.1.2

See [Appendix 1](#) for protocol history, including all amendments.

EMERGENCY CONTACT INFORMATION

In the event of a serious adverse event, the investigator must fax or e-mail the Shire Clinical Trial Serious Adverse Event (SAE) Form within 24 hours to the Shire Pharmacovigilance Department. Applicable fax numbers and e-mail address can be found on the form (sent under separate cover) and below.

Shire Pharmacovigilance SAE Reporting:

United States (US) and Canadian sites: [REDACTED], or e-mail [REDACTED]

European Union (EU) /Rest of World (ROW) sites: [REDACTED], or e-mail [REDACTED]

Premier Research must also be notified of SAEs:

US and Canadian sites: fax [REDACTED], or e-mail [REDACTED]

EU/ROW sites: fax [REDACTED] or e-mail [REDACTED]

For all urgent protocol- or safety-related issues during and outside of business hours, the investigator must contact the Premier Research Medical Monitors:

North America (US and Canada) sites:

[REDACTED], MD, PhD, [REDACTED]

Central phone number: [REDACTED]

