^r For subjects entering the Double-Blind Acute Phase only: Subjects with an unconfirmed diagnosis of UC must have endoscopy performed during the Screening Visit (Visit 1). Subjects with a previously confirmed diagnosis must have endoscopy at the Screening Visit (Visit 1) or at the Baseline Visit (Visit 2) if endoscopy has not been performed within 21 days prior to the Screening Visit (Visit 1).

^s Only for subjects continuing into the Open-label Acute or Double-blind Maintenance Phase.

Table 2: Open-label Acute Phase

Visit	Recommended Telephone call ^a	4	4.1	4.2 ^{b, c, d, e}	6 ^f
Week ^g	Day -7 to -4	Week 2	Week 4	Week 8/Withdrawal	Follow-up
Physical examination				✓	
Height				✓	
Weight				✓	
Vital signs		✓	✓	✓	
Biochemistry (includes C-reactive protein) and hematology				✓	
Pregnancy test (for females of childbearing potential only) ^h		✓	✓	✓	
Pharmacokinetic blood sampling (at participating sites only)				✓	
Urinalysis				✓	
██████████				✓	
Subject e-diary entry: rectal bleeding, stool frequency, DUCS, and Overall Current Health ⁱ		✓	✓	✓	
Assessment of e-diary compliance ^a	✓				
PUCAI (where applicable)				✓	
Average stool frequency ^{j,k,1}		✓	✓	✓	
Average rectal bleeding ^{j,k,1}		✓	✓	✓	
PGA ^{k,1}				✓	
Endoscopy (flexible sigmoidoscopy or colonoscopy), where possible ^k				✓	
IRT entry		✓	✓	✓	
Calculate partial UC-DAI				✓	

Table 2: Open-label Acute Phase

Visit	Recommended Telephone call ^a	4	4.1	4.2 ^{b, c, d, e}	6 ^f
Week ^g	Day -7 to -4	Week 2	Week 4	Week 8/Withdrawal	Follow-up
Investigational product dispensed		✓	✓	✓ ^m	
Investigational product collected and compliance calculated		✓	✓	✓	
Adverse events	✓	✓	✓	✓	✓
Concomitant medication		✓	✓	✓	✓
Re-randomization (subjects entering Double-blind Maintenance Phase only)				✓	

Abbreviations: DUCS=Daily Ulcerative Colitis Scale for children and caregivers; e-diary=electronic diary; IRT= interactive response technology; PGA=Physician's Global Assessment; PUCAI=Pediatric Ulcerative Colitis Activity Index; UC-DAI=Ulcerative Colitis Disease Activity Index.

^a Approximately 4 to 7 days prior to Visit 4 and prior to each subsequent visit (Visits 4.1 and 4.2), it is recommended that site staff telephone the subject or the subject's caregiver to remind them to enter UC-DAI symptoms (rectal bleeding and stool frequency) into the e-diary every night, even if the subject has no symptoms.

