Collection of stool samples for all assessments must occur before administration of any bowel preparations for endoscopy if samples are collected on the same day as bowel preparation administration. Stool samples collected for culture may be processed by local laboratories; however, results from the central laboratory analysis will prevail and will be entered into the eCRF.

Subjects without a confirmed diagnosis of UC:

Endoscopy (flexible sigmoidoscopy or colonoscopy), including biopsies taken for confirmatory histology, must be performed during the period of the Screening Visit (Visit 1). The biopsies taken for confirmation of UC diagnosis will be sent to the site's local laboratory. Confirmatory results to verify the subject's UC diagnosis must be received prior to the Baseline Visit (Visit 2) for randomization.

Subjects with a historical diagnosis of UC:

Subjects who have been diagnosed with UC (endoscopic and histologic reports of diagnosis are available) prior to the Screening Visit (Visit 1) will be considered to have a historical diagnosis of UC. For subjects who have had endoscopy within the 21 days prior to screening, if the endoscopy is consistent with UC, the subject may proceed to the Screening Visit (Visit 1) with a historical diagnosis of UC. The subject can be randomized once the endoscopy confirms the diagnosis of UC. The histologic confirmation of UC can be available after the Baseline Visit (Visit 2). (See next paragraph below for additional details.)

Subjects who enter the Double-blind Acute Phase:

If a standard of care endoscopy (flexible sigmoidoscopy or colonoscopy, including biopsy) has been performed within 21 days prior to the Screening Visit (Visit 1) and appropriate video or photographs of the procedure were obtained, these assessments may be used in lieu of performing an endoscopy during the period of the Screening Visit (Visit 1) or at the Baseline Visit (Visit 2). The video or photographs of this endoscopy must be de-identified and submitted to the study's central reader for confirmation of study eligibility after informed consent for the study is obtained.

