The local laboratory histology report confirming the diagnosis of UC may be pending upon entry into the study at the Screening Visit (Visit 1); however, the confirmatory histology report must be available before randomization at the Baseline Visit (Visit 2). All other protocol-required assessments (including all laboratory assessments, ie, blood, urine and stool collection) must be performed for the Screening Visit (Visit 1) even if recent results are available.

For subject's whose historical diagnosis of UC was made more than 21 days prior to the Screening Visit (Visit 1), then a study specific endoscopy must be performed during the period of the Screening Visit (Visit 1) or at the Baseline Visit (Visit 2). Biopsies are not required for this endoscopy provided that a histology report with results that are compatible with UC is present in the subject's source documents. The confirmatory histology may have been at any time in the subject's history. If histologic confirmation of the previous UC diagnosis is not available in source documents, the entry endoscopy and confirmatory histology must be performed during the period of the Screening Visit (Visit 1) as for those subjects without a confirmed diagnosis of UC.

Subjects who enter the Double-blind Maintenance Phase directly:

All subjects must have a study endoscopy (flexible sigmoidoscopy or colonoscopy) performed during the period of the Screening Visit (Visit 1) or at the Baseline Visit (Visit 2). Biopsies are not required for this endoscopy provided that a histology report with results that are compatible with UC is present in the subject's source documents. The confirmatory histology may have been at any time in the subject's history. If histologic confirmation of the previous UC diagnosis is not available in source documents, the entry endoscopy and confirmatory histology must be performed during the period of the Screening Visit (Visit 1) as for those subjects without a confirmed diagnosis of UC.

All subjects:

Endoscopic video or photographs will be collected and sent to the study's central endoscopy reader for evaluation of mucosal appearance.

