7.1.1.3 Baseline Visit (Visit 2)

The Baseline visit will take place 3 to 21 days after the first day of the Screening Visit (Visit 1) to allow blood and stool tests to be analyzed, and for collection of e-diary data. An extension to this 3- to 21-day period is allowed only in the case where a repeat endoscopy will be performed during the period of the Screening Visit (Visit 1) (see Section 7.1.1.1).

The ± 3 -day visit window which is applicable to other study visits is not applicable to this visit.

The partial UC-DAI score will be calculated by the site, and the mucosal appearance (endoscopy score) will be evaluated separately to determine eligibility for either the Double-blind Acute Phase or the Double-blind Maintenance Phase. The following criteria will determine the study phase a subject can be eligible to enter:

- Subjects with partial UC-DAI ≥ 2 (with a combined rectal bleeding **and** stool frequency score ≥ 1 **and** PGA=1 or 2) **and** with mucosal appearance (endoscopy score)=2 or 3 will be eligible to enter the Double-blind Acute Phase.

- Subjects with partial UC-DAI ≤ 1 (with rectal bleeding=0 **and** stool frequency ≤ 1 **and** PGA=0) **and** with mucosal appearance (endoscopy score)=0 or 1 will be eligible to enter the Double-blind Maintenance Phase.

Subjects with partial UC-DAI score between 1 and 2 will not be eligible to enter the Double-blind Acute Phase or the Double-blind Maintenance Phase.

Subjects who do not meet all the eligibility criteria for either the Double-blind Acute Phase or the Double-blind Maintenance Phase will be considered screen failures. Subjects may be rescreened after consultation with the medical monitor.

A minimum of 1 score each for stool frequency and rectal bleeding must be available in order to randomize subjects into either the Double-blind Acute Phase or the Double-blind Maintenance Phase (see Section [7.2.1.1](#) for details). Subjects with no symptom score data available will be considered screen failures as these symptom score data are used to calculate the partial UC-DAI score needed for enrollment.

Subjects with a historical diagnosis of UC:

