Endoscopy (flexible sigmoidoscopy or colonoscopy) must be performed at the Baseline Visit (Visit 2) if not performed at the Screening Visit (Visit 1) or within 21 days prior to the Screening Visit (Visit 1) (21 days prior applicable only to subjects entering into the Double-blind Acute Phase directly). Endoscopic video or photographs will be collected and sent to the study's central endoscopy reader for evaluation of mucosal appearance.

Please see a description of criteria used for endoscopic scoring in [Appendix 2](#).

If the results of blood and stool tests or partial UC-DAI score show that the subject is not eligible for the study, he/she will not continue in the study and will be considered a screen failure. No additional data will be captured for these subjects.

Eligible subjects will be randomized to low- or high-dose MMX mesalamine/mesalazine stratified by their weight group at the Baseline Visit (Visit 2). If a subject's weight changes during a study phase, their dose will not change.

Weight groups have the same absolute low and high doses for both the Double-blind Acute Phase and the Double-blind Maintenance Phase (see Section [6.2.3](#)).

Double-blind investigational product will be dispensed to eligible subjects per the procedures detailed in Section [6](#).

Subjects and/or caregivers will be instructed to collect UC-DAI symptoms (rectal bleeding and stool frequency) via e-diary once a day before bedtime for 5 days prior to each study visit in the Double-blind Acute Phase and/or Double-blind Maintenance Phase as applicable. The average stool frequency and rectal bleeding scores will be calculated and be made available to the investigator through a report from the e-diary provider. The average stool frequency and rectal bleeding scores will be added to the PGA score determined by the investigator to calculate the partial UC-DAI. Please see a description of the PGA in Section [7.2.1.1](#) and the UC-DAI in Sections [7.2.1.1](#) and [7.2.1.2](#).

Subjects and/or caregivers will be instructed to complete the DUCS and the Overall Current Health e-diary once a day before bedtime for 5 days prior to each study visit in the Double-blind Acute Phase or Double-blind Maintenance Phase as applicable.

The IMPACT III questionnaire will be completed by children aged 8-17 years via paper at the Baseline Visit (Visit 2). Please see a description of the IMPACT III questionnaire in Section [7.2.4.1](#).

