ⁱ The serum pregnancy test will be performed for all female subjects of childbearing potential at the screening visit (Visit 1) and Week 8/Withdrawal (Visit 3.2). Urine pregnancy tests will be performed at all other visits.

^j Urinalysis performed at this visit only for subjects who are not continuing into the Open-label Acute Phase.

¹ Stool samples collected for culture may be processed by local laboratories; however, results from the central laboratory analysis will prevail and will be entered in the eCRF.

^m Rectal bleeding, stool frequency, DUCS, and Overall Current Health e-diary entry is completed once a day before bedtime every day from the evening of the Screening Visit

Table 5: Double-blind Acute Phase

Visit	1 (Screening)	Recommended Telephone call ^a	2 (Baseline)	3 ^b	3.1	3.2 ^{c, d, e, f}	6 ^g
Week/Month ^h	Day -21 to -3	Day -7 to -4	Week 0	Week 2	Week 4	Week 8/Withdrawal	Follow-up

(Visit 1), preferably for at least the 3 days immediately prior to the Baseline Visit (Visit 2). Rectal bleeding, stool frequency, DUCS and Overall Current Health e-diary entry is completed once a day before bedtime for the 5 days immediately prior to Visits 3, 3.1, and 3.2 of the Double-blind Acute Phase.

^a Global Change in Health to be completed by caregivers of children aged 5-10 years and by children aged 11-17 years; IMPACT III to be completed by children aged 8-17 years only (see Section 4.3).

^b The average stool frequency and rectal bleeding scores will be calculated and available to the investigator through a report from the e-diary provider.

^c Components of the partial UC-DAI.

^d Components of the modified full UC-DAI.

^e For subjects entering the Double-Blind Acute Phase only: Subjects with an unconfirmed diagnosis of UC must have endoscopy performed during the Screening Visit (Visit 1).

Subjects with a previously confirmed diagnosis must have endoscopy at the Screening Visit (Visit 1) or at the Baseline Visit (Visit 2) if endoscopy has not been performed within 21 days prior to the Screening Visit (Visit 1).

^g Only for subjects continuing into the Open- label Acute or Double- blind Maintenance Phase.

Table 6: Open-label Acute Phase

Visit	Recommended Telephone call ^a	4	4.1	4.2 ^{b, c, d, e}	6 ^f
Week ^g	Day -7 to -4	Week 2	Week 4	Week 8/Withdrawal	Follow-up
Physical examination				✓	
Height				✓	
Weight				✓	
Vital signs		✓	✓	✓	
Biochemistry (includes C-reactive protein) and hematology				✓	

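### Protocol 7.1.1.1 ties one mandatory-endoscopy sentence for acute entrants to the date of UC diagnosis, while every other statement of the 21-day rule goes by the date of the last endoscopy (minor)

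*Protocol*

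**What the plan says.** Protocol 7.1.1.1, under its heading for subjects entering the Double-blind Acute Phase, contains two rules.

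- **The waiver.** "If a standard of care endoscopy (flexible sigmoidoscopy or colonoscopy, including biopsy) has been performed within 21 days prior to the Screening Visit (Visit 1") with suitable video or photographs on record, then "these assessments may be used in lieu of performing an endoscopy during the period of the Screening Visit (Visit 1) or at the Baseline Visit". The date of diagnosis is not a condition.
- **The mandatory sentence.** If a subject's "historical diagnosis of UC was made more than 21 days prior to the Screening Visit (Visit 1), then a study specific endoscopy must be performed", in the screening period or at Visit 2. It makes no exception for a recent endoscopy. The text that follows adds that biopsy is not needed at this endoscopy when a compatible histology report, of any age, is in the source documents.

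Three other places state the rule.

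- Protocol 7.1.1.3, under "Subjects with a historical diagnosis of UC", makes endoscopy compulsory at the second visit "if not performed at the Screening Visit (Visit 1) or within 21 days prior to the Screening Visit (Visit 1"). It limits the 21-day allowance to subjects entering the acute phase directly.
- Protocol Table 1, footnote r: "Subjects with a previously confirmed diagnosis must have endoscopy at the Screening Visit (Visit 1) or at the Baseline Visit (Visit 2) if endoscopy" is lacking in the preceding 21 days.
- The copy of that footnote under SAP Table 5 has the same condition: "if endoscopy has not been performed within 21 days prior to the Screening Visit (Visit 1").

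**The concern.** The mandatory sentence and the waiver sit under one heading, apply to the same group and use different clocks. One says must, the other says may. A site reading the mandatory sentence on its own would repeat a bowel preparation and an endoscopy in a child whose recent examination four other places accept.

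The child concerned is foreseeable. The acute-phase criteria provide for children already on 5-ASA who relapse (inclusion criterion 9, exclusion criteria 28 and 29). A known patient may well have been scoped for the current flare shortly before screening. At stake are an unnecessary invasive procedure in a child and uniform practice across sites.

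**Working it through.** No figure in the plan depends on this point, so the check is a comparison of texts.

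**Which date each place uses, for acute entrants**

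| Place | Clock for the 21 days |
|---|---|
| Protocol 7.1.1.1, waiver | last endoscopy |
| Protocol 7.1.1.1, mandatory sentence | UC diagnosis |
| Protocol 7.1.1.3 | last endoscopy |
| Protocol Table 1, footnote r | last endoscopy |
| SAP Table 5, copied footnote | last endoscopy |

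The count is one place by diagnosis and four by endoscopy.

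**Applying both clocks to the four possible cases** (days before Visit 1; a recent endoscopy is taken to meet all the waiver conditions)

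| Case | Diagnosis | Last endoscopy | Mandatory sentence | Other four places |
|---|---|---|---|---|
| 1 | 21 or fewer | 21 or fewer | not triggered | study endoscopy not needed |
| 2 | more than 21 | more than 21 | study endoscopy | study endoscopy |
| 3 | more than 21 | 21 or fewer | study endoscopy | study endoscopy not needed |
| 4 | 21 or fewer | more than 21 | silent | study endoscopy |

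Case 4 will be rare, because diagnosis is itself established by endoscopy (inclusion criterion 6). It is also not a contradiction, since the mandatory sentence is merely silent there. The rules conflict only in case 3.

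**Example of case 3.** A child was diagnosed 2 years ago and had a standard of care endoscopy, with biopsy and usable images, 10 days before Visit 1. By endoscopy date, 10 is within 21, so no new endoscopy is needed. By diagnosis date, 2 years exceeds 21 days, so one is mandatory. The difference is 1 − 0 = 1 bowel preparation and endoscopy.

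**Who is outside the conflict.** Direct maintenance entrants must all have a study endoscopy (7.1.1.1), and subjects without a confirmed diagnosis must be scoped during screening.

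**Intent.** The Amendment 5 summary of changes, used here only as evidence of intent, describes the window by endoscopy: "Expanded the window for acceptance of historical endoscopy results from 7 days to 21 days prior to the Screening Visit".

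**The case against.** The best defence is that the two rules form a general requirement and its exception. Both refer to the same period, the screening period or Visit 2. The waiver comes first, has no limit on date of diagnosis, and says in terms that the recent endoscopy stands in place of a study one. On this reading the example child is simply exempt, and the sentence lacks only a word such as *otherwise*. Section 7.1.1.1 also links a historical diagnosis to an endoscopy in the 21 days before screening, which suggests that the drafters had the diagnostic endoscopy in mind. This is probably what was meant, and it is why the point is minor. It does not remove the defect, because the exception is not written into the sentence that says must.

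A second defence is that the waiver covers only a recent diagnostic endoscopy, leaving older diagnoses to the mandatory sentence. The waiver's mention of biopsy, its allowance for pending histology, and the remark in 7.2.1.2 that timing depends on UC history give this some support. It fails on 7.1.1.3 and footnote r. These give the 21-day allowance expressly to subjects with a historical or previously confirmed diagnosis, which includes the children the mandatory sentence would send for endoscopy.

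A reader might also infer that a site using the waiver risks being recorded as deviating. The documents do not support that. SAP 5.4 has the sponsor's study team classify deviations before database lock, and nothing suggests it would count use of a written waiver as one.

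**Conclusion.** The sentence is wrong as written, and the error is minor. It conflicts with four other statements of the rule in exactly one situation: an acute entrant diagnosed more than 21 days before Visit 1 who has a qualifying endoscopy within those 21 days. The cost is one avoidable bowel preparation and endoscopy per such child at a site that follows the sentence literally, and none at a site that follows the other places.

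The number of such children cannot be derived. The documents do not say how many acute entrants have a recent standard of care endoscopy, and the 21-day window dates only from Amendment 5 (10 April 2017) in a study planned for 2013 to 2018.

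Two stronger readings are tempting and should be resisted.

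- **That the trial's results are affected.** The definition of the primary endpoint, the analysis, the sample size and the error rates are the same under either clock.
- **That 7.1.1.3 and footnote r are defective because they restate the waiver with fewer conditions.** Section 7.1.1.3 goes straight on to require images for the central reader, and a schedule footnote need not repeat every detail. Adding the waiver's biopsy condition to them would do harm: a child with long-confirmed UC and a recent, well-imaged endoscopy without biopsy is exempt under those texts now and would then have to be scoped again.

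The conclusion rests on the wording alone and assumes that the endoscopy date is the intended clock, as four of the five places and the amendment summary indicate.

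**What to change.** Make two changes, both in Protocol 7.1.1.1.

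1. Replace the mandatory sentence with one that goes by endoscopy, for example: *A subject with a historical diagnosis of UC who has had no standard of care endoscopy with suitable video or photographs in the 21 days before Visit 1 must have a study specific endoscopy, in the screening period or at Visit 2.*
2. Add to the waiver: *Biopsy at the standard of care endoscopy is needed only if a histology report compatible with UC is not already in the source documents.* This matches what the section already says about biopsy at the study endoscopy.

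With these changes all five places agree in all four cases: cases 1 and 3 need no study endoscopy, cases 2 and 4 need one. The existing requirement for endoscopy with histology during screening, when no histology is on file, stays. So do Section 7.1.1.3, footnote r and the SAP copy.

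The cost is one replaced sentence and one added sentence, by clarification letter or in the next amendment. No data collection or analysis changes, and the SAP needs no revision.
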